1. SYNOPSIS

TITLE	Treatment of multiple gingival recession defects with a coronally advanced flap or a modified tunnel technique and a volume stable three-dimensional xenogenic collagen matrix: a monocentric randomized clinical trial.
TRIAL LOCATION	PI: [name] [name] Dipartimento di Odontoiatria – Ospedale San Raffaele Direttore: [name] [name]
STUDY OBJECTIVES	To compare the outcomes of two muco-gingival surgery techniques, the modified coronally advanced flap (MCAF) for multiple recession defects (Zucchelli & [name] 2000) and the modified coronally advanced tunnel technique (MCAT) (Aroca 2013), performed in the Department of Periodontology of San Raffaele Hospital with the results reported in the literature. Secondarily, the study will evaluate whether patients report a preference in terms of discomfort and perception of aesthetics between the two surgical techniques.
STUDY DESIGN	Single center, National study, Comparative, Randomized, Open label
STUDY POPULATION	Main selection criteria: patients requiring root coverage procedures from the Dental Clinic of San Raffaele Vita-Salute University will be enrolled in the study. Inclusion criteria: multiple (i.e., at least 2) Miller Class I and/or II gingival recessions located in the maxillae, good general health, healthy periodontal conditions (FMPS and FMBS <25%). Exclusion criteria: smoking >10 cigarettes/day, nursing and pregnant female, contraindication against oral surgical interventions and against use of Fibro-Gide Total expected number of patients: 36 (18 for each group)
STUDY PROCEDURES	Recessions will be randomly treated by means of MCAF + CM or MCAT technique + CM. The following measurements will be recorded at baseline (prior to surgery), at 90, 180 and 360 days: Gingival recession depth (REC in mm), Keratinized tissue width (KTW in mm), Gingival thickness (GT in mm), Pocket probing depth (PPD in mm), BoP (Bleeding on Probing, PI (Plaque Index).
STUDY DEVICE	Fibro-Gide
STATISTICAL CONSIDERATIONS	Hypothesis tested: no statistically significant differences are observed with respect to the clinical parameters CRC, at 12 months between the two treatment modalities (i.e., MCAF + CM or MCAT technique with CM). Sample size calculation: the needed number of patients to be enrolled in this study is 17 for the test group MCAF + Fibro-Gide and 17 for the MCAT + Fibro-Gide. However, the number of patients will be increased of 1 patient for each arm considering the possibility of dropout, so the required number will be 18 for each group. Primary method of analysis: the significance of the difference within each group and between groups before and after treatment will be evaluated with the paired samples t-test or two independent samples t-test, as appropriated, regarding all numerical data (REC, KTW, GT, PPD, percentage of root coverage and VAS scale). Fisher's exact test will be applied for categorical data (frequency of complete root coverage). Differences will be considered statistically significant when the p-value was <0.05.
DURATION OF STUDY PERIOD	Global: 2 years Per patient: 1 years

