4.2. Secondary outcomes

- percentage of root coverage (RC %) at 3, 6 and 12 months
- keratinized tissue width (KTW) at 3, 6 and 12 months
- gingival thickness (GT) at 3, 6 and 12 months
- post-surgical pain (PP),
- amount of drug intake after surgery
- patient perception of aesthetics at 6 and 12 months
- color match (blending), contour (correct outline of the gingival margin at adjacent teeth), contiguity (evaluated based on the visible confluence between the treated area and the adjacent soft tissues), degree of keloid formation scored at the 1-year post-surgical evaluation will be measured by an expert periodontist.
- duration of surgery (from anesthesia to last suture).

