5. STUDY DESIGN

5.1. Description of the protocol

The present research is a monocentric prospective parallel randomized controlled clinical trial.

Patients presenting multiple gingival recessions in the maxillae will be enrolled in the study after having signed an informed consent. Recessions will be treated by means of two mucogingival surgery techniques: modified coronally advanced flap (MCAF) and modified coronally advanced tunnel technique (MCAT), in association with the use of a collagen matrix (CM).

An allocation sequence by means of a computer-generated random list will be created and a sealed opaque envelope will contain the type of treatment assigned to each patient. The opaque envelope will be opened immediately after performing anesthesia.

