7.2. Surgical procedures

Two experienced practitioners ([name] and [name]) will perform the surgical session according to the technique as presented by Zucchelli & [name] 2000 and Aroca et al. 2013.

- Modified coronally advanced flap (MCAF)

After local anesthesia, a horizontal incision is made to include one tooth on each side of the teeth to be treated. The horizontal incision of the envelope flap consists of oblique sub-marginal incisions in the interdental areas, incisions which continue with the intra-sulcular incision at the recession defects. Each surgical papilla (SP) is dislocated with respect to the anatomic papilla by the oblique sub-marginal interdental incisions; in particular, the surgical papilla mesial to the flap midline are dislocated more apically and distally, while the papilla distal to the mid-line are shifted in a more apical and mesial position.

The envelope flap is raised with a split-full-split approach in the coronal-apical direction: the surgical papilla is dissected in a split-thickness manner, while gingival tissue apical to the root exposures is raised in a full-thickness manner (to provide that portion of the flap critical for root coverage with more thickness). Finally, the most apical portion of the flap is elevated in a split-thickness manner to facilitate the coronal displacement of the flap.

The portion of the root exposure with loss of clinical attachment (gingival recession plus probeable gingival sulcus/pocket) are mechanically treated with the use of curettes and EDTA is applied for 2 minutes.

The remaining tissue of the anatomic interdental papilla is de-epithelialized to create connective tissue beds to which the surgical papilla are sutured.

A sharp dissection into the vestibular lining mucosa is then carried out to eliminate muscle tension. Flap mobilization is considered “adequate” when the marginal portion of the flap is able to passively reach a level coronal to the CEJ at each single tooth in the surgical site. The flap, in fact, should be stable in its final position even without the sutures.

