7.5. Follow-up

Patients will be followed for 12 months after surgery.

At 7 ± 2 days post-surgery – general examination, photographic picture of the treated site questionnaire about post-operative pain.

At 14 ± 4 days post-surgery – suture removal, photographic pictures of the treated site

At 1 month ± 7 days post-surgery – general examination, photographic picture of the treated site

At 3 months ± 15 days post-surgery - general examination, photographic picture of the treated site, measurements of the following parameters: Gingival recession depth (REC in mm), Keratinized tissue width (KTW in mm), Gingival thickness (GT in mm), Pocket probing depth (PPD in mm), BoP, PI.

At 6 ± 1 months post-surgery - general examination, photographic picture of the treated site, evaluation of the aesthetic outcome, measurements of the following parameters: Gingival recession depth (REC in mm), Keratinized tissue width (KTW in mm), Gingival thickness (GT in mm), Pocket probing depth (PPD in mm), BoP, PI.

At 12 ± 2 months post-surgery - general examination, photographic picture of the treated site, evaluation of the aesthetic outcome, measurements of the following parameters: Gingival recession depth (REC in mm), Keratinized tissue width (KTW in mm), Gingival thickness (GT in mm), Pocket probing depth (PPD in mm), BoP, PI.

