7.6. Investigator training

Five subjects not involved in the study, each showing a pair of single-rooted contra-lateral teeth with recessions $>$ of 2 mm on the mid-buccal aspect of each tooth, will be used to calibrate the examiner. The examiner will evaluate the subjects on two occasions 24 h apart. Calibration will be accepted if 90% of the recordings could be reproduced within a difference ≤ 0.5 mm (Aroca 2010).

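### Open-label trial with no stated masking of the 1-year aesthetic scorer or the follow-up recession examiner, leaving the aesthetic scores, RC% and the primary CRC open to avoidable observer bias

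*Combined protocol and SAP*

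**What the plan says.** The synopsis gives the design as "Single center, National study, Comparative, Randomized, Open label" and adds nothing about masked assessment.

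Two kinds of assessor appear in the plan:

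- **Aesthetic scorer.** Section 4.2 lists colour match, contour, contiguity and keloid as secondary outcomes: "degree of keloid formation scored at the 1-year post-surgical evaluation will be measured by an expert periodontist". Contiguity is "evaluated based on the visible confluence between the treated area and the adjacent soft tissues".
- **Clinical examiner.** Section 7.5 schedules REC at 3, 6 and 12 months without saying who reads it. Section 7.6 calibrates one examiner: "The examiner will evaluate the subjects on two occasions 24 h apart", and "Calibration will be accepted if 90% of the recordings could be reproduced within a difference ≤ 0.5 mm".

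Section 7.2 has two practitioners who "will perform the surgical session according to the technique as presented by" two cited papers. The plan does not say whether either of them also examines or scores.

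Allocation is by a computer-generated list and sealed envelopes (section 5.1): "The opaque envelope will be opened immediately after performing anesthesia". Photographs are already planned for the final visit (section 7.5): "At 12 ± 2 months post-surgery - general examination, photographic picture of the treated site, evaluation of the aesthetic outcome".

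**The concern.** Open label is understandable for the surgeons, who must know the technique. It does not explain why nothing is said about the people who judge the result, since they can be masked at least in part.

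The aesthetic items are expert judgements, and the plan gives no scoring scale to anchor them. RC% depends on a reading in fractions of a millimetre. CRC has no operational definition in the plan. I take it, as its name implies, to come from the same REC reading, so the primary outcome is exposed as well as the secondary ones.

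The safeguards that exist do other work. The envelope protects assignment, and the flow chart puts the baseline readings at screening, before randomization. Neither reaches the follow-up visits. Calibration uses five subjects outside the study and asks whether one examiner repeats their own readings, so it cannot show whether that examiner reads the two arms differently. Readings taken with knowledge of the arm cannot be masked afterwards.

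**Working it through.** **Inputs from the plan.** 17 per arm before dropout, SD 10 points, difference 10 points, alpha 0.05, power 80% (section 8.1); t-test for RC% and Fisher's exact test for CRC (section 8.3). Two-sided testing is assumed. Every bias size and CRC rate below is also an assumption.

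**Reproducing the plan's figure.** The noncentrality is λ = difference / (SD·√(2/n)). With n = 17, SD·√(2/n) = 10·√(2/17) = 3.43. A 10-point difference gives λ = 2.92 and, with 32 df and critical value 2.037, power 0.807. The exact solution is 16.71, hence 17 per arm. The sample size is not disputed here.

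**RC%, uncapped.** With no true difference, a systematic between-arm reading shift takes the place of the difference:

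- shift 0: rejection 0.050
- shift 2.5: λ = 0.73, rejection 0.109
- shift 5: λ = 1.46, rejection 0.293

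**RC%, capped at 100%.** A completely covered patient cannot be read above 100%. If a fraction p is at 100%, the variance is at least p/(1−p)·(100 − mean)². An SD of 10 therefore requires mean ≥ 100 − 10·√((1−p)/p), which is 90.0, 91.8 and 93.5 for p = 0.5, 0.6 and 0.7. I simulated 100,000 trials per case with mass p at 100% and a beta distribution for the rest (a single value where SD 10 leaves no spread). One arm was shifted and then capped:

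| p complete | mean | no shift | +5 (realised shift) | −5 |
|---|---|---|---|---|
| 0.5 | 90 | 0.057 | 0.128 (2.5) | 0.302 |
| 0.5 | 95 | 0.040 | 0.075 (1.7) | 0.370 |
| 0.6 | 92 | 0.051 | 0.089 (2.0) | 0.279 |
| 0.6 | 95 | 0.041 | 0.070 (1.6) | 0.365 |
| 0.7 | 93.5 | 0.050 | 0.067 (1.5) | 0.285 |
| 0.7 | 95 | 0.044 | 0.061 (1.4) | 0.343 |

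The ceiling absorbs most of an upward shift and hardly any of a downward one.

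**CRC, one yes/no result per patient.** Fisher's exact test, 17 v 17, full binomial enumeration, true rate p in both arms, misread fraction m = 0.25. Upward misreading in one arm changes its rate to p + (1−p)m. Opposite misreading also changes the other arm's rate to p(1−m).

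| p | no bias | upward, one arm | opposite, both arms |
|---|---|---|---|
| 0.5 | 0.024 | 0.064 | 0.215 |
| 0.6 | 0.022 | 0.045 | 0.213 |
| 0.7 | 0.020 | 0.035 | 0.215 |
| 0.8 | 0.019 | 0.026 | 0.240 |

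With m = 0.10, the upward case gives 0.020-0.030 and the opposite case 0.045-0.050.

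**Aesthetic items.** No scale or SD is given, so no figure can be computed.

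**The case against.** The best case for the plan is that no direction of bias is evident. Both arms receive the same matrix, both techniques are routine in the department, and there is no untreated comparator. Section 8.1 does call MCAF the test group, so a preference cannot be excluded, but none is shown. This stands: the point concerns exposure to bias, and the documents do not show that bias will occur.

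It can also be said that the primary outcome is robust. Misreading in one direction in one arm takes Fisher rejection above 0.05 in only one of the eight modelled cases (p = 0.5, m = 0.25), and the values above 0.2 need 25% misreading in opposite directions at once. That is fair as far as it goes. A reader might then infer that CRC is safer than RC%. The calculations do not support that ranking, because one bias is in points and the other is a misread fraction, and the two are not matched. A uniform downward shift would by itself turn every complete patient incomplete. CRC is also modelled per patient only, while section 8.3 plans tooth-level analysis too.

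Two further readings are tempting and unsupported. One is that the surgeons grade their own work. The plan names the roles differently and does not say whether they overlap, and personal names were removed from the public text, so this is only not stated. The other is that the 0.5 mm calibration tolerance measures the possible bias. It is a limit on the repeatability of single readings and says nothing about a shift between arms.

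**Conclusion.** The concern holds in this form: the trial is open label, the reviewed text masks neither the 1-year aesthetic scorer nor the follow-up REC examiner, and neither the envelope nor calibration fills the gap. The aesthetic scores, RC% and CRC are open to observer bias that could be partly avoided.

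Its size and direction cannot be determined from the documents. The false-positive rates above show only what assumed biases would do. A modest shift can matter for RC%, particularly a downward one. One-sided misreading of CRC has a small effect and opposite misreading a larger one. The aesthetic part, where judgement enters most, cannot be quantified. The plan should be changed before follow-up readings begin, but open label is a disclosed choice and this is not a fatal defect.

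**What to change.** 1. **Sections 4.2 and 7.5.** Have the planned expert periodontist score the 12-month aesthetic items from the photographs already scheduled for that visit, taken in one fixed view, coded, in random order and without the allocation. If keloid cannot be judged from a photograph, score it chairside and label it unmasked.
2. **Section 7.6.** Within existing staff, make the follow-up REC examiner someone who did not operate and has no access to the envelope or the operative record. If that is not possible, report REC, RC% and CRC as unmasked; this discloses the bias but does not remove it.
3. **Synopsis and section 5.1.** Keep the open-label description for surgeons and patients, and state which assessments are assessor-masked.

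The cost is coding the photographs and keeping the operative record apart, with no extra visit and no second reader. The aesthetic items may currently be meant for chairside scoring, and photographs may not show everything that the chairside view does. Masking may also be imperfect if the MCAF incision lines or the composite stops described only for MCAT are still visible at 12 months.

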2. FLOW-CHART

Evaluation	Screening phase	Study phase						End of study
	Screening	Surgery	Post treatment follow-up					
		Day 0	Day 7±2	Day 14±4	Day 30±7	Day 90±15	Day 180±30	Day 360±60
Demographic data	X							
Inclusion/Exclusion criteria	X							
Previous medical history	X							
Informed consent	X							
Clinical examination	X							
PPD, BoP, PI	X					X	X	X
REC, KTW, GT	X					X	X	X
Oral hygiene instructions	X	X		X				
Treatment								
Randomization		X						
Mucogingival surgery		X						
Use of Fibro-Gide		X						
Compliance			X	X	X	X	X	X
Suture removal				X				
Photography		X	X	X	X	X	X	X
Pain assessment (VAS)			X					

3. INTRODUCTION AND RATIONALE

Gingival recession is defined as the exposure of the root surface due to the displacement of the gingival margin apical to the cement-enamel junction (CEJ) (Armitage 1999; Wennstrom 1996). It was estimated that >20% of the population presents one or more tooth surfaces exhibiting recessions (Albandar and Kingman, 1999). The development of gingival recessions can often be associated with mechanical factors (trauma caused by excessive tooth brushing, orthodontic therapy or piercing), or inflammatory periodontal disease (Graziani 2014). The exposed root surfaces are frequently associated with esthetic complaints, root hypersensitivity and difficulties in achieving optimal plaque control (Cairo 2017).

The progression of gingival recessions should be evaluated in individuals with a high level of plaque control (Matas 2011).

Furthermore, a recent systematic review assessed the prognosis of untreated gingival recessions and found that only 21.9% of sites with gingival recession at baseline did not increase in recession severity during a 2-year follow-up period, and that 79.3% of patients showed an increase in the number of recession defects (Cairo 2017; Chambrone 2016).

Results from systematic reviews indicate that at single Miller (Miller, 1985) Class I and II gingival recessions complete root coverage (CRC) can predictably be obtained when using the modified coronally advanced flap (MCAF) technique, with and without soft tissue grafting and/or biologic agents, such as an enamel matrix derivative (Cairo 2014; Chambrone 2010).

On the other hand, the treatment of multiple gingival recessions appears to be more challenging for the clinician and due to limited evidence, no recommendation can be made to support the selection of one technique over another (Tonetti 2014); but modified CAF and tunnel approaches show higher level of complete root coverage (CRC) (Graziani 2014).

During the discussion of a recent meta-analysis, Graziani reported that despite the “ideal” treatment is not yet identified, there are some indirect suggestions from the analyzed data that, in comparison to the traditional CAF approach, the use of additional grafting, modifications of the flap technique or tunnel variation with connective tissue graft (CTG) may improve clinical results (Graziani 2014).

Findings from a long-term study, suggest that, in patients with a high standard of oral hygiene, enrolled in a regular maintenance care program, shallow recessions may further deteriorate over a period of 10 to 27 years. On the other hand, treatment of contra-laterally located recessions by means of gingival-augmentation techniques showed long-term stability and a tendency for coronal displacement of the gingival margin with a reduction in recession depth (Agudio 2009). These results are in line with those from a 5-year follow-up split mouth study comparing the clinical outcomes of the modified coronally advanced flap (MCAF) alone, versus the coronally advanced flap plus connective tissue graft (CAF + CTG) in the treatment of multiple gingival recessions (Pini-Prato 2010). Over a short period (e.g., up to 6 months), both treatments resulted in comparable outcomes in terms of root coverage. However, at the 5-year follow-up, the sites treated with CAF alone demonstrated an apical relapse of the gingival margin, whereas the sites grafted with CTG showed not only stability, but even a coronal improvement of the gingival margin, as compared to the 6-month results (Agudio 2009; Pini-Prato 2010).

CTG harvesting is often associated with increased patient morbidity, prolonged surgical time and the possibility of postoperative complications such as bleeding, numbness and sensibility changes at the donor area (Aroca 2013; Buff 2009; Reiser 1996). Various allografts or replacement biomaterials have been developed instead of a connective tissue graft in order to reduce patient morbidity (Aroca 2013; Thombre 2013; Cordaro 2012; Aroca 2009). A newly developed porcine-derived bio-resorbable

collagen matrix (CM) (Fibro-Gide) has been recently introduced as an alternative to CTG in periodontal plastic surgery.

These mucogingival surgical techniques are routinely used to treat recessions by clinicians of Department of Periodontology of Dental Clinic of San Raffaele Hospital and they are present in the list of dental services provided with code “ODCMCM”.

4. STUDY OBJECTIVES

The aim of this study will be to compare the outcomes of two muco-gingival surgery techniques, the modified coronally advanced flap (MCAF) for multiple recession defects (Zucchelli & [name] 2000) and the modified coronally advanced tunnel technique (MCAT) (Aroca 2013), performed in the Department of Periodontology of San Raffaele Hospital with the results reported in the literature. Secondarily, the study will evaluate whether patients report a preference in terms of discomfort and perception of aesthetics between the two surgical techniques.

4.1. Primary outcome

- percentage (%) of complete root coverage (CRC) at 12 months

4.2. Secondary outcomes

- percentage of root coverage (RC %) at 3, 6 and 12 months
- keratinized tissue width (KTW) at 3, 6 and 12 months
- gingival thickness (GT) at 3, 6 and 12 months
- post-surgical pain (PP),
- amount of drug intake after surgery
- patient perception of aesthetics at 6 and 12 months
- color match (blending), contour (correct outline of the gingival margin at adjacent teeth), contiguity (evaluated based on the visible confluence between the treated area and the adjacent soft tissues), degree of keloid formation scored at the 1-year post-surgical evaluation will be measured by an expert periodontist.
- duration of surgery (from anesthesia to last suture).

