7.4. Post-operative procedures

Post-surgically, all patients will be given antibiotics for 6 days and were instructed to rinse their mouth with a 0.2% chlorhexidine solution, three times a day for 1 min. for 1 months.

Patients will be instructed to avoid brushing in the operated area until 2 weeks after surgery and instructed in mechanical tooth cleaning using a soft toothbrush.

All patients will be recall after 1, 2 and 4 weeks. They will be further recalled 3, 6 and 12 months after surgery for professional oral hygiene procedures and measurements.

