8.3. Statistical Methods

Statistical analysis will be performed using commercially available software (STATA) or R environment (www.r-project.org). Both patient- and tooth-level analysis will be performed for each parameter. Therefore, mean values and standard deviations (SD), as well other descriptive statistics, for the clinical variables will be calculated for each patient per treatment.

A mixed model will be built to take into account the variability due to patient and tooth factors differentially.

Accordingly, the significance of the difference within each group and between groups before and after treatment will be evaluated with the paired samples t-test or two independent samples t-test, as appropriated, regarding all numerical data (REC, KTW, GT, PPD, percentage of root coverage and VAS scale).

Fisher's exact test will be applied for categorical data (frequency of complete root coverage).

P-values will be computed by means of permutation methods to avoid any distributional assumptions or asymptotical approximation. Differences will be considered statistically significant when the p-value was <0.05 .

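### Do the aesthetic ratings and post-surgical drug intake need fuller definitions in the protocol before they can be analysed?

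*Combined protocol and SAP*

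**What the plan says.** Three bullets of Section 4.2 are involved.

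- The patient's own view of the result: "patient perception of aesthetics at 6 and 12 months".
- A professional rating of colour match, contour, contiguity and keloid formation, "scored at the 1-year post-surgical evaluation will be measured by an expert periodontist".
- "amount of drug intake after surgery", with nothing further.

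The first bullet and post-surgical pain serve the secondary objective in Section 4, which asks "whether patients report a preference in terms of discomfort and perception of aesthetics between the two surgical techniques".

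The visit list in Section 7.5 has the entry "evaluation of the aesthetic outcome, measurements of the following parameters" at both 6 and 12 months, without a rater. At the day 7±2 visit it lists "photographic picture of the treated site questionnaire about post-operative pain". Section 7.4 states that "all patients will be given antibiotics for 6 days" and adds a chlorhexidine rinse; it names no pain-relief drug.

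The flow-chart has a pain VAS row, but no row for aesthetics or drug intake. Section 8.3 applies t-tests to numerical data, in a list that ends with "percentage of root coverage and VAS scale", applies Fisher's exact test to categorical data, and obtains p-values by permutation.

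**The concern.** Section 4.2 implies three aesthetic evaluations per patient, whereas Section 7.5 has two undivided lines. At 12 months one line has to cover ratings by two people, so a site could complete one and treat the task as done. A patient rating missed at that visit could not be obtained afterwards. No scale is stated, and the only VAS identified elsewhere is the one for pain. In an open-label trial, an undefined subjective score also leaves room to choose its form after the data have been seen.

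Drug intake is thinner still. If it were taken as a running total at the day 7±2 visit, it would cover 5 days in one patient and 9 in another. It is also unclear whether the antibiotic given to everyone would count. What is at stake is the quality of the evidence on the secondary objective, since discomfort and aesthetics are all that this objective covers.

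**Working it through.** **What depends on these outcomes.** The plan's one design figure is 17 per arm (Section 8.1), from a difference of 10, an SD of 10, α = 0.05 and 80% power. An exact two-sample t-test calculation, taken as two-sided because the plan does not say, gives 16.71, hence 17, with power 80.7%. No aesthetic or drug-intake quantity enters it. The null hypothesis in Section 8.2 concerns complete root coverage only.

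**Aesthetics, sections compared.**

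| Evaluation | Section 4.2 | Section 7.5 | Flow-chart |
|---|---|---|---|
| Patient, 6 months | rater and time given | aesthetic line at 6 months | no row |
| Patient, 12 months | rater and time given | aesthetic line at 12 months | no row |
| Periodontist, 12 months | rater, time and four items given | same line at 12 months | no row |

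With 36 patients, Section 4.2 implies 36 × 3 = 108 ratings. The Section 7.5 lines number 36 × 2 = 72, a difference of 36. That difference arises only if one line is taken to mean one rating. Section 7.5 lists what happens at a visit, and one entry at 12 months can cover both raters named in Section 4.2. The times agree throughout, so there is no contradiction and the 36 is not a count of lost ratings.

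A missing flow-chart row does not show that an outcome goes uncollected. Duration of surgery is also a secondary outcome without a row, yet Section 7.2 says it will be recorded.

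**Drug intake.** Suppose, although no section says so, that intake is a total since surgery taken at the day 7±2 visit. The period covered runs from 5 to 9 days, a ratio of 9/5 = 1.80. If daily intake halves every h days (assumed), a day-9 total divided by a day-5 total is (1 − 2^(−9/h)) / (1 − 2^(−5/h)).

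| Pattern of intake (assumed) | Day 9 / day 5 |
|---|---|
| Stopped by day 5 | 1.00 |
| h = 1 | 1.03 |
| h = 2 | 1.16 |
| h = 3 | 1.28 |
| h = 4 | 1.36 |
| Constant | 1.80 |

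The range of 0% to 80% comes from the supposed method and the assumed pattern, not from the plan. It also describes the spread between patients, not a difference between arms. Both arms share the same visit window. Unless visit timing depends on technique, varying dates add noise to a randomised comparison without shifting it. The antibiotic course is the same for every patient, so it does not by itself separate the arms.

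**Analysis.** Section 8.3 covers numerical data by a two-sample comparison and categorical data by Fisher's exact test, with permutation p-values that need no distributional assumption. Whichever form the aesthetic ratings or drug count take, one of these applies. The word preference in the secondary objective is loose, because each patient receives one technique. Sections 4.2 and 8.3 already lead to a comparison of ratings between arms, so rewording it would alter no result.

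**The case for a change.** The strongest case for a change is that an outcome's definition belongs in the protocol, because it fixes what is compared. These outcomes carry the secondary objective, the trial is open label, and the wording would cost little: a scale, a counting period and a few flow-chart rows at existing visits.

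Much of this stands as description. No scale for the patient rating, no score range for the periodontist's items and no definition of drug intake appear anywhere in the document. Section 8.3 names neither an aesthetic score nor drug intake, and its VAS is tied to no outcome. A missed patient rating at 12 months would indeed be lost. The periodontist's score is less exposed, since photographs are taken at that visit, although the plan does not say that scoring may use them.

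What does not stand is the step from missing detail to faulty result. The case report form (Sections 9.3 and 10.2) and the day-7 questionnaire (Section 7.5) are not reproduced, and they are the usual place for scales, units and recording periods. A substitute definition also has a cost. Counting days with any pain-relief drug, for example, would score one tablet a day the same as six, and so would replace the amount named in Section 4.2 with a different outcome.

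**Conclusion.** No change to the plan follows. This is a gap in detail that the study forms and a sensible analyst can fill: two raters named in Section 4.2, visit times that agree with Section 7.5, and a between-arm test in Section 8.3 for either kind of data. No rule in the plan is shown to produce a wrong answer or to bias the comparison of techniques.

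The size is small. Only secondary outcomes are touched; complete root coverage at 12 months and the sample size are not. Neither the 36-rating difference nor the 0% to 80% range is a measured effect.

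The conclusion rests on two assumptions: that the case report form and questionnaire, which the document does not show, specify the instruments and the drug-intake period; and that the timing of the day-7 visit does not differ systematically between arms. If the forms proved silent too, these outcomes would be reported with less precision and more caution, but the trial's main conclusion would be the same.
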